STATISTICAL METHODS	
The primary efficacy variable is the percent change from baseline in Week 12 global face total lesion count, defined as the sum of inflammatory lesions (papules and pustules), open comedones, and closed comedones.
 
For the primary efficacy variable, treatment means and between-treatment differences will be assessed by means of a one-way Analysis of Covariance (ANCOVA) model with treatment, gender, and center as factors and the corresponding baseline score as a covariate. Monadic efficacy for a treatment will be concluded if the respective mean percent change from baseline is significantly different from zero. Non-inferiority will be concluded if monadic efficacy is demonstrated in both treatments and the upper bound of the two-side 95% confidence interval of treatment difference (mask with topical gel-cream minus the mask alone) is less than 15 percentage points. If non-inferiority is demonstrated, the testing will proceed to superiority test. Superiority of the mask with topical gel-cream treatment will be concluded if the upper bound of the two-sided 95% confidence interval of the treatment difference is less than 0.
 
Each comparison will be tested at the 0.05 significance level, two-sided. With the stepwise procedure, the familywise error rate is controlled at the 0.05 level.

Protocol Title: A Multi-Center, Evaluator Blinded, Randomized Clinical Study to Evaluate the Efficacy and Tolerance of Two Acne

Treatment Regimens on Subjects with Mild to Moderate Acne Vulgaris

Protocol Number: PS-1701 0314 5529-SACT

Date & Version: 06 March 2017, Final Version 1.0

LIST OF ABBREVIATIONS

Abbreviation	Definition
AE	Adverse Event
AHA	Alpha Hydroxy Acid
AIDS	Acquired Immunodeficiency Syndrome
ANCOVA	Analysis of Covariance
CRF	Case Report Form
DPR	Designated Physician Representative
EDC	Electronic Data Capture
EIU	Exposure in Utero
FDA	US Food and Drug Administration
GMP	Good Manufacturing Practices
HIPAA	Health Insurance Portability and Accountability Act
HIV	Human Immunodeficiency Virus
ICD	Informed Consent Document
ICH GCP	International Conference on Harmonisation Good Clinical Practice
ID	Identification
IEC	Independent Ethics Committee
IGA	Investigator Global Acne
IP	Investigational Product(s) (i.e. test products)
IRB	Institutional Review Board
ITT	Intent-to-Treat
LED	Light-Emitting Diode
LOCF	Last Observation Carried Forward
OCMS	Office of Consumer Medical Safety
OTC	Over-the-Counter
PI	Principal Investigator

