8.2.1. Analysis of Primary Variable

The primary efficacy variable is the percent change from baseline in global face total lesion count at Week 12. The total lesion count is the sum of inflammatory lesions (papules and pustules), open comedones, and closed comedones.

The following comparisons will be performed:

1. Mask alone treatment Week 12 vs. baseline
2. Mask with topical gel-cream treatment Week 12 vs. baseline
3. Mask with topical gel-cream treatment vs. mask alone treatment for non-inferiority
4. Mask with topical gel-cream treatment vs. mask alone treatment for superiority

To evaluate the efficacy of the mask alone treatment and the mask with topical gel-cream treatment, statistical comparisons for the primary variable will be based on a stepwise procedure starting with comparisons #1 and #2, which evaluate the monadic efficacy of mask alone treatment and the mask with topical gel-cream treatment, respectively. If both comparisons are significant, testing will proceed to comparison #3 to evaluate the non-inferiority of the mask with topical gel-cream treatment to the mask alone treatment; otherwise, comparison #3 will be exploratory. The difference between treatment groups will be computed as the mask with topical gel-cream treatment minus the mask alone treatment, and non-inferiority will be concluded if the upper bound of the two-side 95% confidence interval is less than 15 percentage points. If the mask with topical gel-cream treatment is demonstrated to be non-inferior to the mask alone treatment, then testing will proceed to comparison #4; otherwise, comparison #4 will be exploratory.

Comparison #4 will evaluate the superiority of the mask with topical gel-cream treatment versus the mask alone treatment. Superiority will be concluded if the upper bound of the two-sided 95% confidence interval of the treatment difference is less than 0.

Each comparison will be tested at the 0.05 significance level, two-sided. With the stepwise procedure, the familywise error rate is controlled at the 0.05 level.

For the primary efficacy variable, treatment means and between-treatment differences will be assessed by means of an Analysis of Covariance (ANCOVA) model with treatment, gender, and center as factors and the corresponding baseline score as a covariate.

If the global face total lesion count is missing at Week 12 for more than 5% of the subjects, the missing value will be imputed by using the last observation carried forward (LOCF) method.

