4.5. Covariates

For the primary efficacy variable and secondary efficacy variables, treatment means and between-treatment differences will be assessed by means of an Analysis of Covariance (ANCOVA) model with treatment, gender, and center as factors and the corresponding baseline score as a covariate.

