5. HANDLING OF MISSING VALUES

For the analysis of the primary efficacy endpoint, if the global face total lesion count is missing at Week 12 for more than 5% of the subjects, the missing value will be imputed by using the last observation carried forward (LOCF) method.

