6.3. Statistical Methods

6.3.1. Method for Primary Efficacy Endpoint

The mean percent change from baseline in global face total lesion count at Week 12 within the mask with topical gel-cream treatment cell and the mask alone treatment cell will each be tested using a one-sample t-test.

If both of the above comparisons are significant, the non-inferiority of the mask with topical gel-cream treatment to the mask alone treatment will be evaluated; otherwise, this comparison will be exploratory. Treatment means and between-treatment differences will be assessed by means of an ANCOVA model with treatment, gender, and center as factors and the corresponding baseline score as a covariate. The difference between treatment groups will be computed as the mask with topical gel-cream minus the mask alone treatment, and non-inferiority will be concluded if the upper bound of the two-side 95% confidence interval is less than 15 percentage points.

If the mask with topical gel-cream treatment is demonstrated to be non-inferior to the mask alone treatment, the superiority of the mask with topical gel-cream treatment versus the mask alone treatment will be evaluated. Superiority will be concluded if the upper bound of the two-sided 95% confidence interval of the treatment difference is less than 0.

Impact of center on treatment effect will be assessed in a separate analysis by including the center-by-treatment interaction in the ANCOVA model above. Summary statistics will be presented by treatment and center with no statistical comparison between treatments within a center.

If the global face total lesion count is missing at Week 12 for more than 5% of the subjects, the missing value will be imputed by using the last observation carried forward (LOCF) method. In addition, a sensitivity analysis will be performed using a repeated measure mixed model based on the observed data. The model will include the baseline score as the covariate and terms for treatment, gender, center, visit, baseline-by-visit, and treatment-by-visit interactions. The covariance matrix will be assumed unstructured.

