6.4.2. Efficacy Analyses

All efficacy analyses will be based on the Full Analysis Set which will be the primary analysis. As a secondary analysis, the primary efficacy endpoint will be analyzed based on the Per-Protocol Analysis Set.

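### Once more than 5% of Week 12 counts are missing, last observation carried forward decides non-inferiority and superiority, while the mixed model already in the SAP is only a sensitivity analysis

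*SAP*

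**What the plan says.** Protocol 8.2.1, SAP 5 and SAP 6.3.1 carry the same rule. The condition is "If the global face total lesion count is missing at Week 12 for more than 5% of the subjects"; the consequence is that "the missing value will be imputed by using the last observation carried forward (LOCF) method". The denominator of the 5% is not defined.

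The primary analysis is an ANCOVA with treatment, gender, center and baseline (Protocol synopsis and 8.2.1; SAP 4.5 and 6.3.1). On the analysis set, SAP 6.4.2 states: "All efficacy analyses will be based on the Full Analysis Set which will be the primary analysis". Non-inferiority (comparison #3) needs an upper 95% limit below 15 points for gel-cream minus mask alone. Superiority (#4) needs it below 0 and is tested only after #3 succeeds.

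SAP 6.3.1 adds that "a sensitivity analysis will be performed using a repeated measure mixed model based on the observed data", with treatment-by-visit and baseline-by-visit terms and unstructured covariance. The Protocol does not mention this model. The visible text does not justify carrying forward, give an expected dropout rate, or say what happens if the two analyses disagree. The Success Criteria are redacted, so a further decision rule cannot be excluded.

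**The concern.** Lesion counts are taken at Weeks 2, 4, 8 and 12, so a Week 2 count can stand in for a 12-week outcome. This distorts the arm difference in two situations: (a) the difference is still changing over visits; (b) the response is still developing and one arm loses more subjects.

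The direction varies:

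- **Equal loss, growing difference:** the estimate is pulled toward zero. If gel-cream is worse, false non-inferiority becomes more likely. If it is better, superiority power falls.
- **Gel-cream faster but level at Week 12:** gel-cream is favoured.
- **Developing response, more loss on mask alone:** both claims become too easy.
- **Developing response, more loss on gel-cream:** both claims become too hard.

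Unequal loss is plausible. Only one arm adds a product with its own weighed-use rule that can lead to withdrawal (Protocol 6.7), and lack of efficacy and adverse events are listed withdrawal reasons (Protocol 7.3.2). The first between-arm claim, and the superiority test that depends on it, would rest on a method whose error depends on features nobody knows in advance.

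**Working it through.** **Inputs from the documents.** SD 30, margin 15, planned true difference -5, superiority difference -15, 45 completers per arm, up to 136 enrolled (Protocol 8.4).

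**Planned power reproduces.** The standard error is 30 × √(2/45) = 6.32.

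- Non-inferiority: 20/6.32 - 1.96 = 1.20, giving 88.5% (87.9% with the t distribution); the protocol states 87%.
- Superiority: 15/6.32 - 1.96 = 0.41, giving 66.0% (65.0% with t); the protocol states 65%.

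The sample size is not at issue.

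**Trigger.** 5% of 136 is 6.8, so 7 missing counts fire it if all 136 are enrolled and counted. The binomial probability of 7 or more is 52% at a true missing rate of 5% and 99% at 10%. The enrolment plan tolerates (136 - 90)/136 = 33.8% loss, which is a ceiling and not a forecast.

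**Bias formula.** With d an arm's dropout share and g its mean at the carried visits minus its Week 12 mean, bias = d(gel) × g(gel) - d(mask) × g(mask). To illustrate, assume mask-alone means of -10, -20, -32 and -40, dropout split equally after Weeks 2, 4 and 8, and 68 per arm (standard error 30 × √(2/68) = 5.14).

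- *Growing disadvantage 2.5, 5, 10, 15, equal loss.* The carried difference averages 17.5/3 = 5.83, so bias = d × (5.83 - 15) = -9.17d. That is -1.83 at 20% loss and -3.10 at 33.8%. False non-inferiority is Φ(-1.96 + 1.83/5.14) = 5.4%, and 8.7% at 33.8%. A simulation of 4,000 runs gave 5.5% and 8.1%; the mixed model gave 2.6% for both.
- *Identical curves, loss 10% gel-cream and 30% mask alone.* The response still to come is 40 - 62/3 = 19.33, so bias = (0.10 - 0.30) × 19.33 = -3.87. Simulated false superiority was 10.5%, against 2.3% for the mixed model.
- *Constant difference of 15, equal 33.8% loss.* The estimate was 14.9, so there is almost no bias.

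**Main simulation.** 10,000 runs per scenario, with the ANCOVA and mixed model as in SAP 6.3.1. Assumptions not in the documents: 68 per arm, correlation 0.7 between visits, mask-alone Week 12 mean -40, and loss spread evenly over the four intervals and unrelated to outcome. Subjects with no post-baseline count were left out. The mixed model used a t reference on Week 12 completers minus 5, because the SAP names no method. Shares of the Week 12 effect at Weeks 2/4/8/12 were: linear 17/33/67/100, intermediate 38/63/88/100, plateau 70/90/100/100. Monte Carlo error is about 0.16 point near 2.5% and 0.5 point near 50%.

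Equal loss of 10/20/34% (entries in %):

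| Quantity | Curve | Carried forward | Mixed model |
|---|---|---|---|
| False non-inferiority, true +15 | linear | 3.3/4.6/6.6 | 2.5/2.7/2.7 |
| | intermediate | 3.1/3.5/4.2 | 2.6/2.3/2.3 |
| | plateau | 2.6/2.9/3.4 | 2.5/2.4/2.5 |
| Non-inferiority power, true -5 | linear | 95.3/93.0/90.3 | 96.0/94.7/92.5 |
| | intermediate | 96.2/94.6/93.0 | 96.3/94.7/92.2 |
| Superiority power, true -15 | linear | 74.5/65.6/54.5 | 80.2/76.8/72.0 |
| | intermediate | 77.1/73.1/64.9 | 79.5/77.2/71.4 |
| False superiority, gel-cream only faster | intermediate vs linear | 3.3/4.6/6.8 | 2.3/2.5/2.6 |

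With identical linear curves and 34% loss the bias cancels: both methods give 2.5% false superiority.

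Unequal loss of 12 vs 8, 25 vs 15 and 40 vs 27%:

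| Larger loss on | Quantity | Curve | Carried forward | Mixed model |
|---|---|---|---|---|
| mask alone | False non-inferiority, +15 | linear | 4.5/8.0/12.7 | 2.3 to 2.8 |
| | | intermediate | 3.5/5.8/7.2 | 2.3 to 2.8 |
| | | plateau | 2.7/3.4/3.6 | 2.3 to 2.8 |
| mask alone | False superiority, 0 | linear | 3.4/5.3/7.3 | 2.3 to 2.6 |
| | | intermediate | 3.0/4.1/4.9 | 2.3 to 2.6 |
| | | plateau | 2.9/3.1/3.4 | 2.3 to 2.6 |
| gel-cream | Superiority power, -15 | linear | 67.6/50.1/33.2 | 79.4/77.1/71.8 |
| | | intermediate | 74.1/62.8/51.3 | 79.3/77.0/71.9 |

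**Other assumptions.** With 25 vs 15% loss (more on mask alone), a mask-alone mean of -20 gives false superiority of 4.1% (linear) and 3.3% (intermediate); a mean of -60 gives 7.2% and 5.5%. The direction also held at correlations of 0.4 and 0.9.

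**Outcome-related dropout** (one arm only, odds doubling per 30 points worse, 20% loss per arm, intermediate curve). If mask-alone leavers depend on the last observed value, false non-inferiority is 5.1% carried forward and 2.5% with the mixed model. If gel-cream leavers depend on the unseen value, it is 5.5% and 4.7%, and false superiority is 4.0% and 4.7%. Neither method is safe in that last case.

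**The case against.** The preferred model is already prespecified and will be reported, together with a per-protocol analysis and separate Week 2, 4 and 8 results, so a disagreement would be visible. Sites also seek final procedures from early leavers (Protocol Table 1 footnote d; 7.3.2). This lowers the weight but does not remove the point. The mixed model does not carry the decision, the per-protocol set contains completers only, and a final visit at withdrawal still yields an early count.

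The size of the harm cannot be derived from the documents; curve, mean, correlation and dropout are all assumed. This stands. At 10% equal loss the error is only 2.6% to 3.3%. With a plateau it never exceeds 3.6% in the equal-loss and mask-alone-loss scenarios. The 12.7% figure is a stress case.

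With equal loss and gel-cream better, carrying forward is conservative for superiority, and non-inferiority power stays above the planned 87%. This also stands for those cases. It does not cover a gel-cream that is worse or merely faster, or heavier loss on mask alone.

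The mixed model is not uniformly safer. It relies on missing at random, and in one equal-loss scenario carrying forward has slightly more power (93.0% against 92.2%).

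**Conclusion.** The concern holds. On the visible text, the carried-forward ANCOVA decides both between-arm claims once the trigger fires, and its error depends on response shape and dropout balance. Under modest loss the effect is small: one-sided error of about 3% to 5% instead of 2.5%. With unbalanced loss on a still-developing response it is larger, and superiority power can fall well below that of the mixed model. With identical curves and equal dropout, or an early plateau, there is little or no harm. The direction held across the means and correlations tried; the sizes rest on assumed curves and dropout. The mixed model held its nominal error in every scenario where data were missing at random. This is worth correcting, but it is not a fatal flaw.

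**What to change.** Make the Week 12 treatment contrast from the SAP 6.3.1 mixed model primary for #3 and #4, with the same terms, unstructured covariance and a stated degrees-of-freedom method. Remove the 5% trigger for these comparisons. Keep the carried-forward ANCOVA as a sensitivity analysis. Add a tipping-point analysis that progressively worsens missing gel-cream values, because withdrawal for lack of efficacy or adverse events may break missing at random.

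The wording to change is in the Protocol synopsis and 8.2.1, and in SAP 4.5 ("For the primary efficacy variable and secondary efficacy variables, treatment means and between-treatment differences will be assessed by means of an Analysis of Covariance"), 5 and 6.3.1. The within-arm means in #1 and #2, which "will each be tested using a one-sample t-test", can stay as they are: at an assumed -40, SD 30 and 45 per arm, t = 40/(30/√45) = 8.9.

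The cost is wording, one added analysis and approval of a protocol amendment (Protocol 10.1). At 34% equal loss and a true +15, the 95% half-width is 11.6 points, against 10.8 to 11.2 carried forward, so 0.4 to 0.8 points wider. Dropping the trigger costs nothing at low loss: at 5% missing (intermediate curve), observed-case ANCOVA and the mixed model give error of 2.3% and 2.4%, and superiority power of 80.4% and 81.5%.

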6.3.2. Methods for Secondary and Tertiary Efficacy Endpoints

6.3.2.1. Acne Lesion Counts

Summary statistics of the global face acne lesion counts (open comedones counts, closed comedones counts, inflammatory acne lesion counts, non-inflammatory acne lesion counts, and total lesion counts analyzed separately), change from baseline, and the percent change from baseline (only for inflammatory lesions, non-inflammatory lesions, and total) will be presented by visit and treatment group. The corresponding 95% confidence interval of mean change from baseline and percentage change from baseline will be calculated within treatment group by visit.

Due to the small number (or zero count) of closed comedones and open comedones at baseline, percent change will not be calculated by subject for these two types of lesions. Instead, percent change from baseline in group mean will be presented for each treatment. This will be calculated as post-baseline mean minus baseline mean divided by baseline mean times 100.

The percent (%) of subjects who had improvement in counts and percent (%) of subject who had worsening in counts will also be provided. A reduction of 1 or more lesion from baseline will be considered an improvement. An increase of one or more lesion will be considered a worsening.

Treatment means and between-treatment differences in change from baseline and percent change from baseline will be assessed by means of an ANCOVA model with treatment, gender, and center as factors and the corresponding baseline acne lesion counts as a covariate. The two-sided 95% confidence interval of the between-treatment difference will be constructed.

[figure not shown]
6.3.2.2. Investigator Global Acne Assessment

Investigator Global Acne Assessment and the change from baseline will be presented by visit and treatment group using summary statistics. The corresponding 95% confidence interval of mean change from baseline will be calculated within each treatment group by visit. The percentage of subjects who had improvement in counts from the baseline (score reduced from baseline by half-point or greater) within each treatment group will also be summarized by visit.

Treatment means and between-treatment differences in change from baseline will be assessed by means of an ANCOVA model with treatment, gender, and center as factors and the corresponding baseline score as a covariate. The two-sided 95% confidence interval of the between-treatment difference will be constructed.

[figure not shown]
6.3.2.3. Investigator Additional Efficacy Assessment

[figure not shown]
The Investigator Additional Efficacy Assessments will be summarized and analyzed similarly to the Investigator Global Acne Assessment. The percentage of subjects who had improvement in counts from the baseline (score reduced from baseline by half-point or greater) within each treatment group will also be summarized by visit.

Protocol # PS-1701 0314 5529-SACT

Statistical Analysis Plan

6.4. Statistical Analyses

The Quantitative Sciences Department at the Sponsor will be responsible for statistical analyses.

[figure not shown]
Summary statistics will be provided by treatment group at each time point. For continuous variables, descriptive summaries will include number of subjects, mean, standard deviation, median, minimum and maximum values. Distributions of categorical variables will be summarized by presenting the number and percent of subjects in each response category.

6.4.1. Demographic and Baseline Characteristics

Demographic and baseline characteristics will be summarized for all randomized subjects as well as for the full analysis set, the per-protocol analysis set, and the safety analysis set. A summary will also be provided by center for all randomized subjects.

6.4.2. Efficacy Analyses

All efficacy analyses will be based on the Full Analysis Set which will be the primary analysis. As a secondary analysis, the primary efficacy endpoint will be analyzed based on the Per-Protocol Analysis Set.

6.4.4. Safety Analyses

The safety analysis will be based on the Safety Analysis Set.

Adverse events will be classified as treatment-emergent or non-treatment-emergent. Treatment-emergent AEs are those AEs not present prior to first study product usage.

The number and percentage of subjects experiencing treatment-emergent adverse events will be summarized by treatment, MedDRA version 20.0 system organ class, and preferred term.

The number and percentage of subjects experiencing treatment-related AEs will be summarized by treatment, MedDRA system organ class, and preferred term. Treatment-related AEs are events evaluated by the investigator as being possible, probable, or very likely related to study product. AEs with an unknown relationship to treatment will be considered to be treatment-related.

The number and percentage of subjects who were discontinued from the study due to adverse events and the number and percentage of subjects experiencing serious adverse events will be summarized by treatment, MedDRA system organ class, and preferred term.

The number of subjects with treatment-emergent adverse events will be summarized by severity (mild, moderate, and severe) for all adverse events and also for treatment-related adverse events. Subjects will be counted only once for each system organ class and preferred term by selecting the most severe event.

Listings of all adverse events will be provided. Treatment-emergent AEs and non-treatment-emergent AEs, if present, will be listed separately.

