4. STUDY DURATION

The study will consist of 6 visits over 12 weeks. Visit 1 (Week 0) will consist of Screening/Baseline and Post-1st Product Usage time points. The Post-1st Product Usage time point should occur within 20 minutes after the initial product usage. Subsequent visits will occur at Week 1 (Visit 2), Week 2 (Visit 3), Week 4 (Visit 4), Week 8 (Visit 5), and Week 12 (Visit 6).

As necessary, Visit 2 may be adjusted \pm 1 day and Visits 3-6 may be adjusted \pm 3 days. All scheduling windows are versus Visit 1.

If a subject misses a scheduled visit but notifies the study site, he/she will be allowed to re-schedule the missed visit if it is within the scheduling window as specified above. If it is outside the scheduling window, the Study Manager should be notified to determine if the visit should be rescheduled outside the scheduling window. Study staff will need to assess subject compliance with IP usage to ensure the missed/ altered visit did not result in lack of compliance. A lack of compliance will be documented as a deviation and the Sponsor should be notified.

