5.2. STUDY POPULATION

5.2.1. Inclusion Criteria

Individuals must meet all of the following inclusion criteria for enrollment into the study:

- a) Subject (and/or his/her legally acceptable representative, as applicable) has read, understood, signed, dated, and received a copy of the Photograph Release and Informed Consent Document (including HIPAA disclosure) after the nature of the study has been fully explained. The legally acceptable representative's consent and the subject's assent must be secured for subjects under the age of 18 years (i.e. 12 – 17 years of age).
- b) Male or female (up to 50% of subjects may be male).
- c) 12 to 40 years old.
- d) Has 10-100 total non-inflammatory lesions (open comedones plus closed comedones), 10-50 total inflammatory lesions, no cysts, and up to 2 nodules (if deemed appropriate by the PI or designee) on the face (see section 7.1.2.4.1).
- e) Has mild to moderate acne vulgaris on the face, as defined by an IGA assessment score of 2, 2.5, 3, or 3.5 using the Modified Cook's Scale (see section 7.1.2.4.2).
- f) Able to read, write, speak, and understand English.
- g) In generally good health as determined by the PI or designee, based on medical history reported by the subject.
- h) Males and females of reproductive potential must agree to practice a medically acceptable form of birth control during the study and for 30 days after study completion. Females must have used such birth control for at least 3 months prior to Visit 1. Medically acceptable forms of birth control that may be used by the subject and/or his/her partner include:
 - o Established use of hormonal methods of contraception (oral, injected, implanted, patch, or vaginal ring).
 - o Barrier methods of contraception with spermicide: condom or occlusive cap (diaphragm or cervical/vault caps) with spermicidal foam/gel/film/cream/suppository.
 - o Intrauterine device or intrauterine system.
 - o Surgical sterilization (e.g., in a monogamous relationship with male partner with vasectomy that has been confirmed effective by sperm count check, tubal occlusion, hysterectomy, bilateral salpingectomy).

Protocol Title: A Multi-Center, Evaluator Blinded, Randomized Clinical Study to Evaluate the Efficacy and Tolerance of Two Acne Treatment Regimens on Subjects with Mild to Moderate Acne Vulgaris

Protocol Number: PS-1701 0314 5529-SACT

Date & Version: 06 March 2017, Final Version 1.0

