10.3.2. Definitions

10.3.2.1. Adverse Event (AE)

An AE is any untoward medical occurrence in a clinical study subject temporally associated with the clinical investigation, whether or not the event has a causal relationship to the subject's participation in the trial. It is therefore any unfavorable and unintended sign (including an abnormal finding), symptom, or disease that occurs during the trial. This can include any occurrence that is new in onset, an aggravation of severity/frequency of a baseline condition, or abnormal results of diagnostic procedures, including laboratory test abnormalities.

Examples of AEs include but are not limited to:

- Abnormal test findings,
- Clinically important symptoms and signs,
- Changes in physical examination findings,
- Hypersensitivity, and
- Progression/worsening of underlying disease.

Protocol Title: A Multi-Center, Evaluator Blinded, Randomized Clinical Study to Evaluate the Efficacy and Tolerance of Two Acne Treatment Regimens on Subjects with Mild to Moderate Acne Vulgaris

Protocol Number: PS-1701 0314 5529-SACT

Date & Version: 06 March 2017, Final Version 1.0

Any change in existing medical condition (Medical History) would be considered an AE and recorded appropriately.

Additionally, they may include the signs or symptoms resulting from:

- Investigational product overdose,
- Investigational product withdrawal,
- Investigational product abuse,
- Investigational product misuse,
- Investigational product interactions,
- Medication errors,
- Investigational product dependency,
- Exposure *in utero*, and
- Study related procedure.

The criteria for determining whether an abnormal objective test finding should be reported as an AE are as follows:

- Test result is associated with accompanying symptoms, and/or
- Test result requires additional diagnostic testing or medical/surgical intervention, and/or
- Test result leads to a discontinuation from the study, significant additional concomitant treatment, or other therapy, and/or
- Test result is considered to be an adverse event by the PI (or designee) or the Sponsor.

Merely repeating an abnormal test, in the absence of any of the above conditions, does not constitute an AE. Any abnormal test result that is determined to be an error does not require reporting as an AE.

Expected Events

All IPs have the potential to cause some skin reactions, including erythema, scaling/peeling, edema, burning/stinging, tightness/dryness, itching, or rash.

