Any signs or symptoms of irritation are considered a clinical endpoint and may or may not be coded as adverse events based on the PI's or trained designee's assessment. Irrespective of whether the sign(s) or symptom(s) is (are) coded as an adverse event, the signs or symptoms must be documented on the clinical evaluation source documentation. If any of these irritation parameters appear to be exacerbated, more than normally associated with use of these types of products, the event will be recorded as an AE. This can only be determined by the PI or trained designee. If a subject is discontinued due to worsening of a sign or symptom (including worsening of the signs and or symptoms recorded as part of the evaluations), then it should be recorded as an AE.

Treatment Emergent AE (TEAE)

A TEAE is defined as any event not present prior to the initiation of the IP. Note that AEs will be summarized for all subjects who signed the ICD (or Assent Form, as applicable), differentiating TEAEs.

AEs are considered serious and require expedited reporting if they meet the definition of a Serious Adverse Event (see below).

Protocol Title: A Multi-Center, Evaluator Blinded, Randomized Clinical Study to Evaluate the Efficacy and Tolerance of Two Acne Treatment Regimens on Subjects with Mild to Moderate Acne Vulgaris

Protocol Number: PS-1701 0314 5529-SACT

Date & Version: 06 March 2017, Final Version 1.0

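### Does the treatment-emergent definition drop worsening of a pre-existing condition, such as acne itself, from the adverse event tables?

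*SAP*

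**What the plan says.** The SAP defines the term in section 6.4.4: "Treatment-emergent AEs are those AEs not present prior to first study product usage". Protocol 10.3.2.1 has the same single limb: "A TEAE is defined as any event not present prior to the initiation of the IP". Neither sentence mentions events that worsen after first use.

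The same Protocol section sets a wide definition of an adverse event. It includes "an aggravation of severity/frequency of a baseline condition", gives "Progression/worsening of underlying disease" as an example, and adds: "Any change in existing medical condition (Medical History) would be considered an AE and recorded appropriately".

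SAP 6.4.4 restricts two outputs to treatment-emergent events: the overall incidence table by treatment and the severity summary. Its tables of treatment-related events, serious events and discontinuations due to adverse events carry no such restriction. All adverse events are listed, with the non-treatment-emergent ones in a separate listing. Protocol 8.3 plans a by-treatment table of all adverse events during the study.

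**The concern.** Acne is universal at entry. Inclusion criterion e reads: "Has mild to moderate acne vulgaris on the face, as defined by an IGA assessment score of 2, 2.5, 3, or 3.5". If the thing that must be absent before first use is the acne, no flare could ever be treatment-emergent, whatever its size or timing. The same would hold for facial redness or dryness that was present at baseline and was made worse by a regimen.

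This would matter in this trial. The gel-cream is the only non-marketed product (Protocol 6.1), only Regimen 2 uses it, and comparing tolerance is part of the objective. Irritation and flare are natural harms to look for. If they went only to a separate listing, the overall adverse event rate would be understated, and a difference between regimens could be missed.

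**Working it through.** No arithmetic applies. The question is what two definitions mean when read together, so the check sets them side by side.

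**Step 1: what must be absent before first use.** In the SAP sentence it is the adverse event. In the Protocol sentence it is the event, and that sentence stands inside the section that defines adverse events. Neither sentence refers to the underlying condition.

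**Step 2: what the adverse event is when acne gets worse.** Under Protocol 10.3.2.1 the worsening is the adverse event. The acne seen at entry is an eligibility requirement. Adverse event reporting starts only at signed consent (Protocol 10.3.3), so acne that existed before then is not a recorded event.

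**Step 3: put the two together.** Take a flare that begins at Week 2. The recorded event is the flare. It did not exist before first use, so it is treatment-emergent. The same reasoning covers baseline redness or dryness that worsens enough to be recorded as an adverse event.

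**Step 4: find what is left over.** The definition gives no explicit place to an event that begins after consent but before first use and then worsens. Protocol section 4 says: "Visit 1 (Week 0) will consist of Screening/Baseline and Post-1st Product Usage time points". Consent and the supervised first use also belong to Visit 1 (Table 1), so the window is part of one site visit. Even there, recording the later worsening as a new event would make it treatment-emergent. Only an update to the severity of the existing record would leave it out.

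**Step 5: suppose the other reading were used.** The table shows where worsening of a baseline condition would appear under each reading.

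| Worsening after first use | Adverse event must be new | Condition must be new |
|---|---|---|
| Judged related, or relationship unknown | Treatment-emergent tables and related-event table | Related-event table by treatment |
| Serious | Treatment-emergent tables and serious-event table | Serious-event table by treatment |
| Led to discontinuation | Treatment-emergent tables and discontinuation table | Discontinuation table by treatment |
| Unrelated or doubtful, not serious, no discontinuation | Treatment-emergent tables | Separate listing only |

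The third row has support in the Protocol, which addresses the case that starts "If a subject is discontinued due to worsening of a sign or symptom" and has it recorded as an adverse event. A flare caused by a product belongs in the first row, which stays visible by regimen on either reading. Only the last row is lost, and those events are by definition the ones least attributed to the products. They would still fall within the all-event table of Protocol 8.3.

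**Step 6: other views of the same harm.** SAP 6.3.2.1 reports the percentage of subjects whose lesion counts rise by one or more, and it compares changes in counts between treatments. SAP 6.3.2.2 does the same comparison for the global acne score. Both measure acne worsening more directly than adverse event coding does.

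**The case for a change.** The strongest case for a change is that the documents never state which reading applies. The programmer or coder must choose, and could choose differently by site or by type of event. The Protocol plans a table of all adverse events, while the SAP's overall table covers treatment-emergent events only, so the boundary of that category carries more weight. A clause on worsening would take one line in each document and need no new data, since the severity of every event is already assessed.

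Part of this stands. Both definitions are silent on worsening, and an explicit clause would do no harm. The difference between the Protocol's table and the SAP's table is also real. It is small in effect, because on the reading in Step 3 the two can differ only through events placed before first use, within Visit 1.

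The rest does not stand. A loss of every acne-worsening event follows only if the condition is put in place of the adverse event, and the text does not do that. The SAP's severity sentence does not say that the summary is by treatment, so a hidden difference between regimens in that output is an inference. The plan for tolerance cannot be judged from the public text, because much of it is blacked out. Protocol 10.3.2.1 does treat signs of irritation as a clinical endpoint, to be documented whether or not they are coded as adverse events. The visible text therefore cannot show that worsened redness or dryness would go unseen.

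**Conclusion.** The concern does not call for a change. Read with the Protocol's own definition of an adverse event, the treatment-emergent rule already takes in a worsening that starts after first use. The gap that remains is an event that begins between consent and first use at Visit 1, then worsens, and is not recorded anew. The documents give no count of such events, but the window is only part of one visit, so few can be expected.

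This rests on two assumptions: that sites record a worsening as its own adverse event with its own onset, as Protocol 10.3.2.1 directs, and that the analyst classifies by that onset. If the second fails, the loss is confined to worsening that is unrelated or doubtful, not serious and not a cause of discontinuation, and those events remain in the listings. The missing clause is a gap that analysts can fill sensibly from the text. The documents do not show that the comparative tables omit worsening or that event rates are understated.
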